7.3 END OF STUDY TREATMENT AND FOLLOW-UP PERIOD

Patients will be followed for 2 years from the initiation of treatment. The imaging studies will be performed at baseline and at week 18, 30, 52, and 104. Patients will continue to be followed thereafter by their treating physicians as per standard of care.

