8. STATISTICAL METHODS

Power Caclulation: From the MIRI study, the 1-year PFS rate for class I and II combined was 43.8% (95% CI: 38.6 - 49.7%) Assuming a one sided alpha of 0.05 and an 85% power to detect an improvement in 1-yr PFS from 40% to 55% we estimate 46 patients will need to be accrued in 2.5 years and followed for an additional 2 years (estimated maximum total of 51 patients). Accounting for a 20% drop out rate, 62 patients will need to be consented. The sample size calculation was based on assumptions of exponentially distributed death times and use of the exponential MLE test (42). Definition of clinical outcomes: PFS is defined as months from treatment started to evidenced progression or death and censored at last follow up without progression, and OS is defined as months from treatment started to death or censored at last follow up if alive.

Analysis plan: For primary objective, the 1-yr PFS and its 95% confidence interval will be estimated by Kaplan-Meier method for all patients, as well as in each stratum defined by p16 and RPA status, but this study is not powered at the level of subgroups. For the secondary objectives, Kaplan-Meier method will be used to assess 1-yr OS, PFS, or pattern of failure, and the incidence rate of acute and late toxicities will be described as frequency and percentage. QOL will be summarized by mean and standard deviation. For exploratory objectives, the predictability of related biomarkers (baseline PDL1 status, T-cell activation biomarkers, CD28 and TCF1 positivity on T lymphocytes and other biomarkers) to clinical

outcomes (OS and PFS) will be explored using both univariate and multivariable Cox proportional hazards model controlling for potential confounders.

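### PFS is censored at last follow-up, not at the last disease assessment, so 1-year PFS would read slightly high if patients stop assessments but stay in contact

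*Combined protocol and SAP*

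**What the plan says.** Section 8 defines PFS as "months from treatment started to evidenced progression or death and censored at last follow up without progression". The same sentence continues: "OS is defined as months from treatment started to death or censored at last follow up if alive". The primary analysis is that "the 1-yr PFS and its 95% confidence interval will be estimated by Kaplan-Meier method for all patients". The benchmark is a fixed rate; the trial is sized for an "improvement in 1-yr PFS from 40% to 55"%.

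Section 7.3 sets the imaging: "The imaging studies will be performed at baseline and at week 18, 30, 52, and 104". Contact is more frequent than that. Section 4.3.1 gives ten maintenance doses at 4-week intervals after radiotherapy, and the Treatment Study Calendar puts a history and physical at each maintenance visit. Sections 3.1.4 and 7.5 follow every patient, including those who stop treatment early, for survival to 2 years from the start of radiation.

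Some provisions work against gaps. The calendar's imaging footnote calls for extra scans when progression is suspected or symptoms warrant. Section 4.3.2 continues tumor assessments when dosing is delayed. Section 7.5 follows patients for response until progression. The documents contain no censoring rule based on assessments, no rule for missed scans and no sensitivity analysis of censoring.

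**The concern.** Any contact can show that a patient is alive, so last follow-up is a sound censoring point for OS. Contact alone does not show that a patient is progression-free. If a patient is no longer assessed but is still seen, or is reached only for survival, the PFS clock keeps running while progression cannot be recorded. That patient stays in the Kaplan-Meier risk set as a non-event.

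In this trial the error can go only one way. There is no control arm to share it, and the estimate is set against a fixed 40%. The definition also leaves the censoring date of the primary endpoint open to interpretation after the data are seen.

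**Working it through.** **1. The plan's own figure.** Inputs from section 8: "Assuming a one sided alpha of 0.05 and an 85% power", 1-year PFS 40% against 55%, exponential times, and "46 patients will need to be accrued in 2.5 years and followed for an additional 2 years".

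- Hazards: −ln(0.40) = 0.916 and −ln(0.55) = 0.598 per year; ratio 0.652.
- Events: (1.645 + 1.036)² / [ln(0.652)]² = 39.4.
- Probability of an event under 55%, with uniform accrual over 2.5 years plus 2 years: 1 − [exp(−0.598×2) − exp(−0.598×4.5)] / (0.598×2.5) = 0.843.
- Patients: 39.4 / 0.843 = 46.8. An exact gamma version gives 46.3.

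The stated 46 is reproduced, and nothing below changes it.

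**2. Can contact outlast assessment?** The scan gaps that bear on a 1-year estimate are 18, 12 and 22 weeks (weeks 0–18, 18–30, 30–52). If the first maintenance dose falls 4 weeks after the week-6 dose (assumed), the ten doses fall at weeks 10 to 46. A patient who completes treatment and then misses the week-52 scan has a last scan at week 30 and a last visit at week 46. That leaves 16 weeks without imaging. Survival follow-up can extend the gap to 2 years.

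**3. Size of the effect.** The simulation used 200,000 patients per scenario and the protocol scans ±2 weeks. Scans were shifted by 2 weeks because treatment starts at week −2. Kaplan-Meier was read at 12 months. These assumptions are not in the documents:

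- 0 to 20% of patients stop scans, at a uniform time in year 1.
- Contact then lasts 4 weeks, 12 weeks, or to 2 years.
- 0 or 50% of progressions are found clinically.
- 15% of PFS events are deaths without progression.
- Median survival after progression is 12 months.

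The difference below is last-contact minus last-assessment censoring, over true 1-year PFS of 40% and 55%.

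| Stop scans in year 1 | Difference, points |
|---|---|
| 0% | 0 |
| 5% | 0.3 to 0.7 |
| 10% | 0.7 to 1.5 |
| 20% | 1.4 to 3.0 |

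Examples at 20% stopping and true 40%:

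- Contact for 4 weeks, progression found by scan only: 52.3% against 50.6%.
- Contact to 2 years, progression found by scan only: 54.1% against 51.4%.
- Contact to 2 years, half of progressions found clinically: 49.4% against 46.5%.

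A second simulation, read at 52 weeks, widened the upper ends to about 1 point (5% stopping) and 3.4 points (20% stopping).

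**4. Error rather than difference.** With complete scans the same schedule gives about 52% (scan only) or 46.5% (half found clinically). Against those values, with 20% stopping, the last-contact rule is about 0.3 to 2.9 points high and the last-assessment rule 0 to about 1.5 points low.

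**5. Scale.** The standard error at n = 46 is √(0.40×0.60/46) = 7.2 points. The largest difference is 3.4 / 7.2 = 0.47 of a standard error.

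**The case against.** The strongest reply is that scans are not the only disease assessment. The event is not limited to imaging, maintenance visits include an examination, and post-operative patients without gross disease need no tumor measurements. Last follow-up without progression could then mean the last visit at which absence of progression was recorded. That reading is possible. The parallel OS wording and the lack of any assessment-based rule point the other way. Two tenable readings of a primary endpoint are themselves a reason to specify it.

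The existing safeguards also stand. They reduce the effect, but they do not reach a patient without symptoms who is no longer scanned.

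Comparability is a fair point as well. The documents do not say how PFS was censored in the MIRI cohort. If it was at last contact, the stated rule is the like-for-like one.

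A reader might infer more than the documents support in three places:

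- **That a fifth of treated patients will miss scans.** Section 8 says "Accounting for a 20% drop out rate, 62 patients will need to be consented". This raises 51 to 62 (51 × 1.2 = 61.2) and may include people who never start treatment. It is not a rate of missed scans.
- **That the 52-week scan gap matters here.** It runs from week 52 to week 104. Apart from the roughly 2-week offset in the clock, that is after the 1-year endpoint.
- **That the type I error is badly inflated.** With the exponential MLE test and 20% stopping, an extreme calculation rejects a true 40% in about 35% of trials. It keeps those patients at risk to week 104 and never counts their deaths, whereas the protocol counts death as an event. The analysis paragraph also specifies Kaplan-Meier, not that test.

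**Conclusion.** The point holds in conditional form. The stated rule lets unassessed time count as progression-free, and whenever patients stop assessments but stay in contact it gives a higher 1-year PFS than last-assessment censoring. The two rules agree if scans are complete. The difference is about 0.3 to 1 point if 5% stop scans in year 1 and about 1.4 to 3.4 points if 20% stop, which is under half a standard error. The shares are assumed, and the figures rest on the contact and detection assumptions listed in the working.

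This should be corrected because it concerns the primary endpoint of a single-arm trial, its direction is known, and the remedy is short. It does not show that the trial's estimate will be materially wrong.

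**What to change.** In section 8, make three changes:

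- Censor PFS at the last adequate disease assessment showing no progression. Count protocol imaging, or a documented clinical examination where no tumor measurement is required.
- State how progression or death after missed assessments is handled.
- Report last-contact censoring as a sensitivity analysis. This also keeps a like-for-like figure if the MIRI benchmark was censored that way.

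Counting every loss before week 52 as an event is an optional worst-case analysis.

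The cost is a few sentences and possibly a slightly less favourable estimate; the sample size is unaffected. The new rule has its own small downward error, up to about 1.5 points in the scenarios run. It also leaves a larger, separate effect in place. With no missed scans at all, a true 40% reads as about 46.5% to 52% at 12 months, because scans are sparse and the week-52 scan falls about 54 weeks after treatment start.

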Objectives	
Primary Objectives:
 
1- To assess the 1-year PFS for patients with RPA class I and II disease treated with nivolumab and IMRT re-irradiation
 
Secondary Objectives:
 
1- Evaluate the OS of patients treated with re-irradiation and nivolumab 2- Evaluate patient QOL 3- Evaluate patterns of failure including rates of locoregional failure and distant failure 4- Identify and estimate the incidence rate of acute and late toxicities associated with combined re-irradiation and nivolumab followed by nivolumab
 
Exploratory Objectives:
 
 • To identify potential biomarkers related to clinical benefit to concurrent nivolumab and re-irradiation in patients with recurrent HNSCC.

SAEStudy Design	
This will be a phase II single arm study of IMRT re-irradiation in combination with nivolumab in the concurrent and maintenance setting. Patients with RPA class I and II based on the recursive partitioning analysis (RPA) classes reported by Ward et al (ASTRO 2016) will be enrolled. The allowable treatment approaches include IMRT. Based on this analysis, only patients with RPA classes I and II will be included; Class III patients will be excluded.
 
RT will be given as 60-66Gy in once daily fractions (2 Gy per fraction).
 
Nivolumab will be administered 2 weeks prior to the beginning of radiation therapy (1 dose at Week -2) and continue every 2 weeks during radiation (4 doses at Weeks 0, 2, 4, 6) for a total of 5 doses. Nivolumab will then be given every 4 weeks for 10 additional doses for a total of 15 doses of Nivolumab.

Number of Patients	
From the MIRI study, the 1-year PFS rate for class I and II combined was 43.8% (95% CI: 38.6 - 49.7%). Assuming a one sided alpha of 0.05 and an 85% power to detect an improvement in 1-yr PFS from 40% to 55% we estimate 46 patients will need to be accrued in 2.5 years and followed for an additional 2 years (estimated maximum total of 51 patients). Accounting for a 20% drop out rate, 62 patients will need to be consented.

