Test	Pre-therapy (Day -30 to -1 before Nivolumab)	Every 2 weeks during each Nivo cycle before and during radiation	Every 4 weeks during each Nivo cycle for maintenance phase ^k	Wk 18 and 30 disease assessment ^a	Wk 52 (1yr after start of radiation) or at the time of disease progression	Wk 104 (yr 2 after start of radiation) or at the time of disease progression
History and physical ^b	X	X ^k	X ^k	X ^k	X	X
Weight and ECOG PS	X	X ^k	X	X	X	X
Tumor measurement (if applicable)	X			X	X	X
CBC and diff ^c	X	X	X		X	X
Chemistries (Na, Cl, CO2, K, BUN, Creatinine, Ca, Phos)	X	X ^k	X ^k		X	X
Liver function panel ^d	X	X	X		X	X
PT, PTT, INR	X				X	X
TSH	X		X		X	X
Tissue for research purposes - fresh biopsy (paraffin embedded if fresh tissue not available) ^{e, f}	X				X	
Blood for research purposes	X	X		X	X	X
Toxicity assessment ^g	X	X		X	X	X
QOL assessment	X	Wk 6 at completion of radiation		X	X	X
Radiology: 1. PET/CT or 2. CT- or MRI-neck AND CT-chest, CT-abdomen for tumor measurements ^h	X ⁱ			X	X	X

Serum B-HCG ^j	X						
--------------------------	---	--	--	--	--	--	--

^a. Disease assessments may be done +/- 2 weeks of specified time in protocol to allow for scheduling and/or transportation needs of the patient

^b. If Nivolumab or radiation has to be permanently discontinued due to side effects, H&P must be done 4 and 8 weeks after treatment discontinuation.

^c. CBC and diff include WBC, ANC, HCT, HGB, PLT, % lymphocytes, % monocytes, % neutrophils.

^d. Liver function panel includes Alk Phos, total bilirubin, SGOT (AST), SGPT (ALT), total protein.

^e. Fresh biopsy will be obtained before the first treatment when feasible. If tissue is not obtained, it is not considered a protocol deviation.

^f. Participating sites could have restricted number of research specimens (up to 6 draws per patient) depending on financial constraints;

^g. Toxicity assessment: Common Toxicity Criteria (CTC) version 4.03 will be used. All toxicity grades (including grade 1) should be captured on the case report forms. All toxicities that occurred during treatment and until 100 days following completion of therapy should be followed until resolution.

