^h Tumor measurement: The scans may be performed within +/- 2 weeks of intended f/u times (wks 18, 30, 52, and 104). Additional scans should be obtained as clinically indicated if progression is suspected or symptoms warrant further investigation. No tumor measurements are required in the postoperative high risk setting where no gross disease is apparent.

ⁱ. For patients enrolled post salvage surgery, a CT of the Neck and Chest or a PET scan will be required as a baseline study prior to enrollment. The sites can use a simulation CT of the Neck and Chest for this purpose.

^j. Pregnancy test should be done in woman of childbearing age who are sexually active and may potentially be pregnant. Prior to study enrollment, women of childbearing potential (WOCBP) must be advised of the importance of avoiding pregnancy during trial participation and the potential risk factors for an unintentional pregnancy. In addition, men enrolled on this study should understand the risks to any sexual partner of childbearing potential and should practice an effective method of birth control. All WOCBP MUST have a negative pregnancy test within 7 days prior to first receiving Nivolumab. If the pregnancy test is positive, the patient must not receive investigational product and must not be enrolled in the study. In addition, all WOCBP should be instructed to contact the Investigator immediately if they suspect they might be pregnant (e.g., missed or late menstrual period) at any time during study participation. The Investigator must immediately notify BMS in the event of a confirmed pregnancy in a patient participating in the study.

^k. May allow a window of 7 days of delay for labs (CBC diff and Chemistries) and 7 days of delay for nivolumab infusion if nivolumab given every 4 weeks; may also allow a window of 3 days between History, PE and ECOG PS status and nivolumab infusion (regardless of the nivolumab schedule)

TABLE OF CONTENTS

PROTOCOL SYNOPSIS	3
SCHEMA	6
TREATMENT STUDY CALENDAR	7
TABLE OF CONTENTS	9
1. INTRODUCTION.....	11
1.1. MEDICAL BACKGROUND	11
1.1.1. Treatment of Recurrent Locoregionally Advanced Head and Neck Squamous Cell Carcinoma	11
1.1.2. The Role of Reirradiation in HNSCC	12
1.1.3. Immunotherapy in HNSCC.....	12
1.1.4. PD-1 and Nivolumab in HNSCC in the context of radiation therapy.....	13
2. RATIONALE, OBJECTIVES, AND BENEFIT-RISK ASSESSMENT.....	17
2.1. RATIONALE FOR PERFORMING THE TRIAL.....	17
2.2. TRIAL OBJECTIVES	17
2.2.1. Primary Objective.....	17

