2.2.3. Secondary Objectives

- 1- Evaluate the 1-yr OS of patients treated with re-irradiation and nivolumab
- 2- Evaluate patient QOL
- 3- Evaluate patterns of failure including local, regional and distant failure rates at 1yr
- 4- Identify and estimate the incidence rate of acute and late toxicities associated with combined re-irradiation and concurrent and adjuvant nivolumab

Exploratory Objectives:

To identify potential biomarkers related to clinical benefit to concurrent and adjuvant nivolumab and re-irradiation in patients with RSP HNSCC.

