7.5 DURATION OF FOLLOW-UP

For this protocol, all patients, including those who discontinue protocol therapy early, will be followed for response until progression and for survival for 2 years from the start of radiation. All patients must also be followed through completion of all protocol therapy. Patients removed from study for unacceptable adverse events will be followed until resolution or stabilization of the adverse event.

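### Failure by site is assigned to Kaplan-Meier with no event definitions or competing-event rule; if deaths are censored, the 1-year failure rates are overstated

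*Combined protocol and SAP*

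**What the plan says.** The analysis plan in section 8 groups three outcomes under one method: "Kaplan-Meier method will be used to assess 1-yr OS, PFS, or pattern of failure".

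The target is secondary objective 3. Section 2.2.3 words it as "Evaluate patterns of failure including local, regional and distant failure rates at 1yr". The synopsis has "Evaluate patterns of failure including rates of locoregional failure and distant failure", which merges local with regional and gives no time point.

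Section 8 defines two time-to-event outcomes. One is PFS: "PFS is defined as months from treatment started to evidenced progression or death and censored at last follow up without progression". The other is OS. No section defines local, regional, locoregional or distant failure, dates them, gives a censoring rule, or says how simultaneous failures or deaths without failure are handled. Cumulative incidence and competing risks are not mentioned anywhere.

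On follow-up, section 7.5 says that patients "will be followed for response until progression and for survival for 2 years from the start of radiation". Section 7.3 gives the imaging schedule without that limit: "The imaging studies will be performed at baseline and at week 18, 30, 52, and 104". The Treatment Study Calendar has a column headed "Wk 52 (1yr after start of radiation) or at the time of disease progression", and its footnote h adds: "Additional scans should be obtained as clinically indicated if progression is suspected or symptoms warrant further investigation".

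**The concern.** Kaplan-Meier treats a censored patient as someone who could still have the event later. That is reasonable for a patient still in follow-up. It is wrong for one who has died, and, in an analysis of first failure, for one who has already failed elsewhere. How the method behaves depends on a rule that the plan does not give:

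- (a) Deaths censored, patients kept at risk after failing at another site: one minus Kaplan-Meier exceeds the proportion of patients who fail at the site.
- (b) First failures at other sites also censored: the excess is larger.
- (c) Death counted as an event: the curve is survival free of failure at that site, and its complement is a failure-or-death rate.

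None of these returns the proportion failing at each site by 1 year once competing events occur before then. Such events are to be expected: the design assumes that 45–60% of patients progress or die within a year, and section 1.1.2 quotes a 2-year OS of 50% for the better-prognosis classes.

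At stake is whether the failure rates by site can be interpreted. A reader of the report could not tell whether a rate was inflated or was a different quantity altogether. PFS, OS and the sample size are not touched.

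**Working it through.** **The plan's own figures.** The plan states no failure rate by site. Its nearest figure is the sample size, which rests on the same exponential model as the check below. The yearly hazards are −ln(0.40) = 0.916 and −ln(0.55) = 0.598, a ratio of 0.652. On the log-hazard scale, the events needed are (1.645 + 1.036)² / (ln 0.652)² = 39.4. With 2.5 years of uniform accrual and 2 further years of follow-up, the event probability under the alternative is 0.843, so N = 39.4 / 0.843 = 46.8. This agrees with the stated 46 to within one patient.

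**Inputs.** 1-year PFS of 40%, 43.8% and 55% comes from section 8. The shares of first PFS events that are locoregional (s_LR), distant (s_D) and death without failure (s_death) are *assumed*, because the documents give none. Hazards are taken as constant, with no other censoring before 1 year.

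**Formulas**, with λ = −ln(PFS) and k the site:

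- One minus Kaplan-Meier: 1 − exp(−λ·s_k).
- Cumulative incidence of first failure at k: s_k·(1 − PFS).
- Cumulative incidence of any failure at k, with only death competing and the death hazard unchanged after failure elsewhere: s_k/(s_k + s_death) · [1 − exp(−λ·(s_k + s_death))].

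**Worked example.** PFS 43.8%, so λ = 0.8255; assumed split 50/20/30.

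| 1-year quantity | Locoregional | Distant |
|---|---|---|
| One minus Kaplan-Meier | 1 − exp(−0.4128) = 33.8% | 1 − exp(−0.1651) = 15.2% |
| Cumulative incidence, first failure | 0.5 × 0.562 = 28.1% | 0.2 × 0.562 = 11.2% |
| Cumulative incidence, any failure | 0.625 × 0.4834 = 30.2% | 0.4 × 0.3382 = 13.5% |

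Under rule (c) the locoregional figure would be 1 − exp(−0.8 × 0.8255) = 48.3%. That is a different quantity, not a biased estimate of the 30.2%.

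A simulation of this case (n = 46, 4,000 runs) gave average locoregional Kaplan-Meier against cumulative incidence of 33.7% v 28.0% for first failure and 33.8% v 30.2% with only death competing.

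**Range.** Twenty assumed splits were used: 19 with locoregional 40–70%, distant 10–30% and death without failure 15–30%, plus 80/10/10. The overstatement in percentage points is:

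| 1-year PFS | First failure: locoregional | First failure: distant | Only death competing: locoregional | Only death competing: distant |
|---|---|---|---|---|
| 40% | 3.96–6.79 | 2.76–6.03 | 2.03–4.85 | 0.38–2.89 |
| 43.8% | 3.38–5.74 | 2.30–5.08 | 1.73–4.11 | 0.31–2.41 |
| 55% | 2.01–3.34 | 1.30–2.92 | 1.03–2.40 | 0.17–1.35 |

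If the death hazard triples after failure elsewhere, the upper ends of the death-only ranges at PFS 40% become 5.07 and 3.38.

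**Additivity.** At PFS 40% with a 45/30/25 split, the three complements are 33.8%, 24.0% and 20.5%. They add to 78.3%, although only 60% of patients have any event. The corresponding cumulative incidences, 27.0%, 18.0% and 15.0%, add to 60%.

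**Non-constant hazards.** Take yearly hazards for months 0–6 and 6–12 of 0.25 then 0.75 (locoregional), 0.35 then 0.05 (distant) and 0.15 throughout (death). PFS is then exp(−0.85) = 42.7%. Locoregional is 39.3% by Kaplan-Meier against a cumulative incidence of 30.9%, a gap of 8.4 points. Distant is 18.1% against 16.0%. The locoregional-to-distant ratio moves from 1.94 to 2.17.

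**Sampling error.** The 95% half-width around 28.1% is 1.96·√(0.281 × 0.719 / n): 13.0 points with 46 patients and 12.3 with 51.

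**The case against.** The strongest reply is that the plan nowhere says deaths will be censored. What the documents establish is a missing rule, and the direction of the bias follows only once a rule is supplied. That is correct, and the conclusion is worded conditionally. It does not rescue the method, because counting deaths as events gives a failure-or-death rate. Such a rate is a coherent endpoint if labelled so, but section 2.2.3 asks for failure rates at each site.

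A second reply is that the sizes come from assumed splits. This stands. If deaths without failure were only 5% of events, with the rest split 70/30, the death-only excess would be 0.5–0.9 points for locoregional and 0.2–0.5 for distant failure across the PFS range. The illustration also pools local and regional failure, which section 2.2.3 lists separately. The direction does not depend on the split.

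A third is that the documents lean towards first failure, since section 7.5 follows response only until progression. The calendar heading and footnote h are compatible with that reading. Only the unqualified schedule in section 7.3 clearly leaves room for imaging after progression. This is fair, but a leaning is not a definition, and the choice determines which events compete. Likewise, the two wordings of the objective do not conflict, since locoregional is the union of local and regional; aligning them is tidying.

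Finally, the bias is smaller than the sampling error and no test or decision depends on it. That limits the weight of the point. But a confidence interval does not reflect this error, and it costs almost nothing to avoid.

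**Conclusion.** The concern holds. Section 8 names a method that does not estimate the failure rates by site that objective 3 asks for, and leaves out the definitions needed to know what it would estimate. Confidence is high on the omission and on the direction of the error when competing events are censored. The size is illustrative: under constant hazards and the assumed splits, 2.0–6.8 points for locoregional and 1.3–6.0 for distant failure when other first failures and deaths are both censored, and 1.0–4.9 and 0.2–2.9 when only death competes. Other splits or non-constant hazards can fall outside these ranges. The effect on the balance between locoregional and distant failure cannot be predicted from the documents. The plan should be changed, but the consequence is confined to one descriptive secondary objective.

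**What to change.** In section 8, keep Kaplan-Meier for PFS and OS, and replace it for pattern of failure with the 1-year cumulative incidence (Aalen-Johansen) and its 95% confidence interval for each failure type. State the following:

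- what counts as local, regional and distant failure, and how each is dated;
- whether first failure or any failure is analysed;
- that death without the failure is a competing event and, for a first-failure analysis, that other first-failure types are too;
- that simultaneous failures count towards each site involved, or are reported so that site totals can be recovered;
- that only patients alive without the event at last follow-up are censored (and, for first failure, without another first failure).

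Use the same failure categories in the synopsis and section 2.2.3. If any failure is chosen, say in section 7.5 that site-specific follow-up continues after first progression.

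The cost is a few sentences and standard software. The case report form must record site and date of failure if it does not already. A first-failure analysis needs no extra visits; an any-failure analysis needs imaging after first progression to be recorded by site.

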2. RATIONALE, OBJECTIVES, AND BENEFIT-RISK ASSESSMENT

2.1. RATIONALE FOR PERFORMING THE TRIAL

This study seeks to investigate the potential benefit of the addition of adjuvant immunotherapy to IMRT based re-irradiation in RPA Class I and II patients with locoregional recurrent or second primary (RSP) head and neck squamous cancer. Our hypothesis is that nivolumab will lead to an improved disease control in this population at high risk of relapse which will translate into an improved 1 year progression-free survival (PFS) compared to the standard re-irradiation with IMRT. We also believe based on the recent PRO data presented at ESMO 2016, that nivolumab will preserve the quality of life in this heavily pre-treated patient population. Given these initial exciting results in patients with advanced head and neck squamous cancer, there is strong rationale for the addition of PD-1 inhibition to an IMRT re-irradiation backbone. This study explores this combination therapy against the standard IMRT re-irradiation with or without other systemic therapies used in the MIRI cohort.

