4.3.7. Patient Reported Outcomes (PROs)

The FACT-HN and FACT-G (Appendix 2) Quality of Life (QOL) assessments will be performed at baseline, end of IMRT, and weeks 18, 30, 52, and 104. Patients who do not have QOL collected or refuse QOL completion will not be considered a protocol deviation. Paper or electronic questionnaires may be completed by the patient. A copy of the responses needs to be kept in the study subject's research binder.

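### The QOL analysis is a bare mean and SD over a shrinking cohort, so a change in who is measured can be confused with a change within patients

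*Combined protocol and SAP*

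**What the plan says.** Section 2.2.3 lists QOL as a secondary objective in three words, "Evaluate patient QOL", and the synopsis does the same. The rationale in section 2.1 goes further and expresses the belief that "nivolumab will preserve the quality of life in this heavily pre-treated patient population".

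Section 4.3.7 says the FACT-HN and FACT-G "assessments will be performed at baseline, end of IMRT, and weeks 18, 30, 52, and 104". It adds: "Patients who do not have QOL collected or refuse QOL completion will not be considered a protocol deviation". The study calendar marks QOL in its last two columns, but heads the first of them "Wk 52 (1yr after start of radiation) or at the time of disease progression", and the week-104 column carries the same alternative. Section 7.5 says that patients "will be followed for response until progression and for survival for 2 years from the start of radiation"; it mentions no QOL form after progression.

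The analysis, in section 8, is one sentence: "QOL will be summarized by mean and standard deviation". The documents give no key score or time point, change from baseline, confidence interval, completion reporting, or rule for forms missing through death, progression or refusal.

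**The concern.** Whether QOL is preserved is a question about change within patients. A raw mean at a late visit describes only those who filled in a form then. If patients with poorer baseline QOL progress or die sooner, the late respondents were a better-off group from the start, and their mean can sit near the baseline mean of the whole cohort although they have declined.

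The calendar adds a second difficulty. A form taken at an early progression may be filed under week 52 or 104 and averaged with forms taken on schedule, so that the mean belongs to no defined time.

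At stake is how the QOL result can be read: a flat series of means could be reported in support of the belief in section 2.1 when the data do not show it.

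**Working it through.** **Inputs.** From section 8: 1-year PFS of 40% (null) and 55% (target), one-sided alpha 0.05, power 85%, exponential times, 46 patients, accrual over 2.5 years and 2 further years of follow-up. From section 1.1.2: a quoted 2-year OS of 50% for class I and II patients.

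**The plan's own figure first.** The yearly hazards are −ln 0.40 = 0.916 and −ln 0.55 = 0.598. The probability of an event during the study is 0.937 under the null and 0.843 under the target.
- Log-hazard scale: events = ((1.645 + 1.036) / ln(0.598/0.916))² = 39.4, and 39.4 / 0.843 = 46.8, so 47 patients.
- Cube-root scale with separate variances: 45.3, so 46 patients.

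The stated 46 is reproduced, so the exponential rates can be used for attrition.

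**Attrition.** The share progression-free at week w is exp(−hazard × w/52). I ignore the two weeks between the first nivolumab dose and the start of radiation. Out of 46 patients:

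| | Week 18 | Week 30 | Week 52 | Week 104 |
|---|---|---|---|---|
| 1-year PFS 55% | 37 | 33 | 25 (55%) | 14 (30%) |
| 1-year PFS 40% | 34 | 27 | 18 (40%) | 7 (16%) |

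If forms continued after progression, the limit would be survival. A 2-year OS of 50%, taken as exponential, leaves 46 × 0.707 ≈ 33 alive at week 52 and 46 × 0.50 = 23 at week 104. Refusals come on top.

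**Selection effect (illustration).** Let baseline QOL q be standard normal and let no patient's QOL change. Assume that the hazard of progression or death is multiplied by HR for each SD of better baseline QOL, with HR between 0.8 and 0.6, and that patients who have progressed give no form. Neither assumption is in the documents. The probability of remaining is S(q) = exp(−k·HR^q), with k chosen so that the average of S(q) equals the share remaining. The baseline mean of those remaining is E[q·S(q)] / E[S(q)].

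| Share remaining | Source | HR 0.8 | HR 0.6 |
|---|---|---|---|
| 55% | week 52, target PFS | 0.13 SD | 0.28 SD |
| 40% | week 52, null PFS | 0.20 SD | 0.42 SD |
| 30% | week 104, target PFS | 0.26 SD | 0.53 SD |
| 16% | week 104, null PFS | 0.39 SD | 0.77 SD |

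A uniform true decline equal to the tabulated shift would leave the visit mean at the cohort's baseline mean. A larger decline would still show. With 55% remaining, a decline of 0.50 SD would appear as a fall of 0.50 − 0.28 = 0.22 SD to 0.50 − 0.13 = 0.37 SD.

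**Precision.** The 95% half-width of a raw mean, t/√n in SD units, is 0.41 at n = 25, 0.50 at 18, 0.58 at 14 and 0.92 at 7.

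**Timing.** Section 4.3.7 gives fixed weeks only, while the calendar allows the last two assessments at progression. If the calendar is followed, living patients who progress do contribute a form, perhaps when they are doing worse. That pulls the mean down, against the selection effect above.

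**The case against.** A reader might infer that the plan cannot answer its own QOL hypothesis. The documents do not support that. The hypothesis stated in section 2.1 concerns disease control and 1-year PFS. The QOL sentence after it is a belief, and the formal objective is only to evaluate QOL. No QOL test or threshold is set, and a descriptive summary suits a descriptive objective.

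A reader might also infer that the means will be biased upwards. That is not established either. Section 8 does not say that the summary is by visit or of raw scores; a mean and SD of within-patient change would also satisfy it. Forms taken at progression could reduce or reverse the selection. The sizes above depend on an outside hazard ratio, and at week 52 with 25 patients the sampling half-width (0.41 SD) exceeds the whole illustrated shift (0.13–0.28 SD).

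Finally, a mixed model is not a full cure. It assumes data missing at random, which is doubtful when progression and death drive the loss, and without a control arm no model can credit nivolumab with preserving QOL.

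All of this stands, and it limits the point. It does not supply what is missing: a defined quantity, a rule for missing and progression-triggered forms, and a count of who contributed.

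**Conclusion.** The concern holds in a limited form. The stated summary is underspecified. On its most natural reading, raw means of whoever completes a form, it cannot separate changing composition from change within patients. The attrition follows from the plan's own rates: 45–60% of patients have progressed or died by week 52 and 70–84% by week 104, with about half dead at two years on the quoted OS.

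The possible masking at week 52, 0.13–0.28 SD at 55% remaining and 0.20–0.42 SD at 40%, is illustrative. It rests on the assumed hazard ratio of 0.8–0.6 per SD and on the absence of forms from patients who have progressed. Because the calendar may bring some of those forms in, the net direction of bias is uncertain.

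This is a cheap and worthwhile improvement to one descriptive secondary objective. The primary PFS result is untouched.

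**What to change.** In section 8:

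1. Make the QOL summary the within-patient change from baseline in FACT-H&N with a 95% CI, from a mixed model for repeated measures. Paired change at each visit is an acceptable simpler alternative.
2. Place each form by its actual date. Do not pool progression-triggered forms with week 52 or 104, and align the calendar with section 4.3.7 on when these forms are due.
3. Report the numbers alive, expected and completed at each visit.
4. Keep raw means and SDs as description.

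**Cost.** A little more analysis work. No new patients, visits or questionnaires are needed, since baseline and repeated scores are already collected. The missing-at-random assumption should be stated as doubtful at week 104, where 7 to 14 patients may be progression-free, and the report should not attribute preserved QOL to nivolumab in a single-arm study.
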